This phase III trial is planned to provide 90% power to detect a 25% increase in the rate of sustained recovery for an investigational agent compared to placebo at the 0.025, 1-sided level of significance. This requires 843 primary events (i.e., participants who achieve sustained recovery). Randomization of 1,000 participants, equally allocated to each investigational agent and placebo, followed for 90 days is estimated to result in the required number of primary events. The event target may be achieved earlier if more than 1,000 participants are enrolled. Sample size will be evaluated periodically by study team members who are blinded to interim results on treatment difference and may be increased to maintain power for the hypothesized difference in sustained recovery between the investigational agent and placebo.

Population

The study population consists of inpatient adults (\geq 18 years) who have had COVID-19 symptoms \leq 12 days. Initially, enrollment is restricted to disease severity stratum 1. After a pre-specified review by the DSMB for safety and futility, when approximately 150 participants

are enrolled per study arm, eligibility for randomization will be expanded to also include patients in disease severity stratum 2, subject to recommendations by the FDA and DSMB.

Stratification

Randomization is stratified by study site pharmacy; once enrolment is expanded to also include disease severity stratum 2, randomization will also be stratified by disease severity stratum.

Monitoring

An independent DSMB will review interim data on a regular basis for safety and efficacy. An initial futility assessment will be performed after the first 300 participants (150 in the active and 150 in the placebo arms) are enrolled and have Day 5 data; this initial assessment is based on two ordinal outcomes (pulmonary and pulmonary+ outcomes at Day 5). Afterwards, the DSMB will use pre-specified guidelines to identify agents with clear evidence of efficacy for the primary outcome and, if so, recommend unblinding of the trial results for that agent. Conversely, the DSMB may recommend discontinuation of an investigational agent if the risks are judged to outweigh the benefits or if futility assessments indicate that there is low probability that an investigational agent will achieve statistical significance for the primary endpoint of sustained recovery.

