1.3 Randomization

The randomization is described in section 6.1 of the protocol.

Patients will be equally allocated to each investigational agent + SOC or to placebo + SOC. For example, for a study of a single investigational agent, participants will be randomized in a 1:1 ratio to the investigational agent or placebo. If a patient is eligible for two investigational agents and the placebo can be shared, the allocation will be 1:1:1 to investigational agent A, agent B, or placebo. Because the two investigational agents (A and B) may require different placebos

(for example, when infusion volumes differ), the 1:1:1 allocation ratio will be achieved through a two-step randomization procedure: in *step 1*, the participant is randomized 2:1 to "active" versus "placebo"; in *step 2*, the participant is randomized 1:1 to A versus B. With k agents, this can be viewed as an initial k:1 allocation to "active" versus "placebo", followed by a second, even allocation to one of the available agents (for example, if a participant was allocated to "placebo" in step 1, then the step 2 allocation will be 1:1 to "matched placebo for A" versus "matched placebo for B"). For the analysis, the concurrent agent-specific placebo groups will be pooled, resulting in a 1:1 allocation ratio for comparing each investigational agent versus the (pooled placebo) control group. If investigational agents are added or dropped, the allocation ratio to active versus placebo will be appropriately modified, and sample size will be recalculated as appropriate.

Randomization will be stratified by study site pharmacy (several clinical sites may share one pharmacy) and severity of disease at entry; the two disease severity strata are defined in section 1.2 of this SAP.

If more than one investigational agent is being compared with placebo and they have different contraindications, it is possible that a participant is eligible only for a subset of agents.

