Stratification: Tests comparing the investigational agent versus control for primary outcomes and key secondary outcomes will be stratified according to the planned randomization strata (disease severity and site pharmacy), provided participant numbers are sufficiently large. In this analysis plan, "stratification by disease severity" refers to the two disease severity randomization strata described in section 1.2. Initially, participants are enrolled only in disease severity stratum 1, until the investigational agent has passed the initial futility assessment (when 300 participants are enrolled for the pairwise comparison; 150 per study arm) and has been approved to expand enrolment to include participants from both strata 1 and 2. In this SAP, we use the notation "stratification by disease severity and site pharmacy" to denote the following:

- For analyses that include only participants in disease severity stratum 1, analyses will be stratified by site pharmacy.
- For analyses that include participants in both disease severity strata, analyses will be stratified by site pharmacy within each disease severity stratum; this means, the maximal possible number of strata is twice the number of site pharmacies. For analyses where stratification is implemented through addition of indicator variables for strata to the model, the strata would be defined through main effects for disease severity, for site pharmacy, and the interaction between disease severity and site pharmacy.

Because there are many site pharmacies, some strata may be small, particularly early in the trial. In order to avoid loss of power, any stratum that contains too few participants (less than 10-20 participants or events) should be pooled with other strata (of the same disease severity, and preferably within the same country or geographical region). Thus, several small strata may be pooled together, or pooled with a larger stratum.

For time-to-event analyses, if strata are too small for fitting separate baseline hazard functions, strata may be added as a categorical covariate to models instead. Whenever possible, however, analyses should be stratified by disease severity (with separate baseline hazard functions).

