12.1 Associations of Baseline Levels with Clinical Outcomes

For each treatment group, associations of baseline antibody status (negative versus positive), levels of plasma antigen, and levels of viral RNA at study entry, with time to *sustained recovery* through day 90 (primary efficacy outcome) and with important safety outcomes will be assessed.

12.2 Plasma Antigen Levels Through Day 5

Plasma antigen levels over time (Baseline, Days 1, 3, and 5) will be described using the following summary statistics, by treatment group, for all participants with follow-up data, and separately for participants who were nAb negative versus nAb positive at study entry:

• Number and percent of participants with antigen levels < 3 ng/L ("antigen negative"), and number and percent of participants with antigen levels < median antigen levels at

study entry (the cut-point used for subgroup analyses).

- Side-by-side box plots of antigen levels. Antigen levels < 3 ng/L (the lower limit of quantification) will be imputed as 2.9, and antigen levels will plotted on the log₁₀-scale.
- Geometric mean concentrations (GMC) of the antigen levels

Hypothesis 1: Over the first 5 days, antigen levels will decline faster in those receiving the investigational agent compared to those receiving placebo.

Hypothesis 2: The treatment effect (investigational agent versus placebo) on the antigen levels is stronger among participants who are nAb negative at study entry compared with those who are nAb positive at study entry.

To address these hypotheses, treatment groups will be compared for the percentage of participants who are antigen negative (i.e., antigen levels < 3 ng/L) at Days 1, 3, and 5, overall (Hypothesis 1) and within subgroups (Hypothesis 2).

- At each time point, the treatment difference will be estimated using a logistic regression model with the log₁₀-transformed baseline antigen level and disease severity indicator as covariates, and ORs with 95% CIs and p-values will be cited.
- In addition to the treatment comparisons at each time point (Days 1, 3, and 5), longitudinal GEE models will be fitted for the proportion of participants who are antigen negative over time, and slopes over time will be compared between treatment groups. The GEE models will be adjusted for baseline levels and disease severity.

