- In addition to estimating the treatment differences within each subgroup, heterogeneity of the treatment effect across subgroups by baseline nAb status (Hypothesis 2) will be assessed by testing for an interaction between the treatment group indicator and the subgroup indicator for baseline nAb status in an expanded GEE model.
- Unadjusted analysis will also be performed, as sensitivity analysis.

Comment: Within the full study population, treatment comparison will be adjusted for nAb status at study entry by including the nAb status and disease severity indicators as covariates. Within nAb subgroups, comparisons will be adjusted for disease severity.

As secondary analyses, treatment groups will also be compared for the percentage of participants with antigen levels < median antigen level at study entry, as well as for the geometric mean concentration (GMC) of antigen levels.

In order to compare treatment groups for geometric mean concentration (GMC) of antigen levels, antigen levels < 3 ng/L will be imputed as 2.9 ng/L, and the treatment difference will be estimated as the GMC ratio for the investigational agent versus placebo. For this analysis, plasma antigen levels will be log₁₀-transformed, mean differences will be estimated with 95% Cls in ANCOVA models that include the treatment indicator as fixed effect and the baseline log₁₀ antigen level and disease severity indicator as covariates, and the treatment difference will be back-transformed to the original scale to estimate the GMC ratio. These analyses will be performed in the full study population, as well as within subgroups by nAb status. Heterogeneity of the treatment effect across subgroups will be assessed by testing for an interaction between treatment group and subgroup indicator in expanded ANCOVA models for the log₁₀-transformed antigen levels.

12.3 Antibody Levels Through Day 5

Levels of nAb and anti-N antibodies at baseline, Days 1, 3, and 5 will be described using the following summary statistics, by treatment group, for all participants with follow-up data, and separately within subgroups by antibody status (positive versus negative) at study entry. To investigate nAb levels over time, subgroups will be formed by nAb status. To investigate anti-N antibody levels over time, subgroups will be formed by anti-N antibody status. Similar analyses will be performed for anti-Spike IgG antibody levels.

- Number and percent of participants with nAb percent binding ratio

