 > 30% ("nAb positive")
- Number and percent of participants with anti-Spike IgG antibody level
 > 770 ng/mL ("anti-Spike IgG positive")
- Side-by-side box plots of nAb, anti-N, and anti-Spike IgG antibody levels over time
- Median concentrations of the nAb, anti-N, and anti-Spike IgG antibody levels

Comment: The manufacturer of the anti-N antibody assay (BioRad) considers samples with specimen ratios < 0.8 as "antibody negative", and samples with values between 0.8 and 1 as "equivocal". For our analyses, we refer to all samples with specimen ratio < 1 as "anti-N negative".

Treatment groups will be compared for the following outcomes, overall and within subgroups by antibody status at study entry:

- The percentage of participants who are nAb positive (i.e., percent binding ratio
 > 30%) at Days 1, 3, and 5, overall and within subgroups by nAb status at study entry.
- The percentage of participants who are anti-N antibody positive (i.e., specimen ratio 1) at Days 1, 3, and 5, overall and within subgroups by anti-N antibody status at study entry.
- The percentage of participants who are anti-Spike IgG antibody positive (i.e., antibody level
 > 770 ng/mL) at study entry at Days 1, 3, and 5, overall and within subgroups by anti-spike IgG antibody levels at study entry.

Statistical methods are similar to those described for comparing antigen levels over time.

In addition, at Days 1, 3, and 5, treatment groups will be compared for mean antibody levels (nAb, anti-N, and anti-Spike IgG levels), and the mean difference (investigational agent minus placebo) will be estimated with 95% CIs, overall and in subgroups by antibody status, using ANCOVA models that include the treatment indicator as fixed effect, and the baseline antibody level (continuous covariate) and disease severity indicator as covariates. Treatment groups will also be compared for mean change over time using longitudinal mixed effects models, comparing slopes of mean antibody levels over time between treatment groups. Heterogeneity of the treatment effect across subgroups will be assessed by testing for an interaction between treatment group and subgroup indicator in expanded longitudinal mixed effects models.

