- No participants were randomized in disease severity stratum 2 (defined in section 1.2; in particular, stratum 2 included participants requiring invasive mechanical ventilation or ECMO). Therefore, the originally planned stratification of analyses by disease severity stratum can't be carried out. Early in the trial, participants requiring non-invasive ventilation (NIV) or oxygen from a high-flow nasal cannula (HFNC) also were excluded. Beginning July 19, 2021, eligibility was expanded to include participants requiring NIV or HFNC. Considering this expansion of eligibility criteria, a sensitivity analysis will be carried out using a Fine-Gray model that only stratifies by oxygen requirements at baseline. A sensitivity analysis without any stratification will also be carried out.
- A subgroup analysis by calendar date of enrollment will also be carried out (2 subgroups: participants enrolled before July 19, 2021 and at or after July 19, 2021). The cut-point was chosen because on July 19, 2021, the first patient who required HFNC or NIV was enrolled after eligibility was expanded to include such patients.

If the primary comparison of AZD7442 versus placebo for time to sustained recovery shows a significant treatment effect in nAb-negative participants, then major safety, efficacy, and subgroup analyses will be conducted for the nAb-negative participants as well as for the full study cohort.

E-6 Interim Monitoring Guidelines

There are 2 changes to the interim monitoring guidelines described in Section 10.3 of this SAP:

- The information fraction for the Lan-DeMets spending function will be based on the target of 1,228 sustained recoveries, not 843.
- As part of the broad assessment of risk/benefit, the DSMB should consider the findings in nAb negative and nAb positive subgroups. For participants who are nAb negative, greater benefit with the investigational agent is hypothesized.

Comment: The antibody status at baseline was unknown for a large proportion of participants until late in the trial. Therefore, separate interim monitoring boundaries were not planned for this subgroup.

E-7 Subgroup Analyses by Vaccine and Immunosuppression Status

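### The antigen and antibody comparisons in SAP 12.2-12.3 leave out site pharmacy, a randomization factor; if sites differ, the ANCOVA tests are mildly conservative and some power is lost

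*SAP*

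**What the plan says.** **Randomization.** SAP 1.2 (Stratification) states: "Randomization is stratified by study site pharmacy; once enrolment is expanded to also include disease severity stratum 2", severity is added as a second factor. Until then pharmacy is the only factor. SAP 1.3 describes pooling of placebo groups, "resulting in a 1:1 allocation ratio for comparing each investigational agent versus the (pooled placebo) control group".

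**Antigen models (12.2).** The per-day logistic models for antigen-negative status and the secondary ANCOVA on log10 antigen adjust for baseline level and the severity indicator. For the longitudinal models, "The GEE models will be adjusted for baseline levels and disease severity". A comment adds nAb status in the full population and then says: "Within nAb subgroups, comparisons will be adjusted for disease severity".

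**Antibody models (12.3).** Methods follow 12.2. The ANCOVA for mean levels includes treatment "and the baseline antibody level (continuous covariate) and disease severity indicator as covariates". Neither section names pharmacy.

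**Meaning of severity.** In section 3, stratification by disease severity "refers to the two disease severity randomization strata described in section 1.2". For AZD7442, Appendix E-5 reports: "No participants were randomized in disease severity stratum 2". Appendix G does not say whether MP0420 enrolled stratum 2.

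**Reach of the general rules.** Section 3 states: "Tests comparing the investigational agent versus control for primary outcomes and key secondary outcomes will be stratified according to the planned randomization strata". Section 8.3 extends this to the other listed secondary outcomes. Antigen and antibody levels are in neither group. Section 3 also allows for stratified CMH tests of binary outcomes, but 12.2 specifies logistic regression instead.

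**The concern.** When treatment is balanced within pharmacies by design, differences between pharmacies contribute almost nothing to the error of the treatment contrast. A linear model that omits pharmacy still counts those differences as residual noise. Its standard error is then larger than the true one, and the test is conservative.

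The severity indicator does not make up for this. If every participant is in stratum 1 it is constant, and the models then contain no randomization factor at all.

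Precision matters here. Viral RNA is measured at baseline only, so follow-up antigen is the SAP's direct look at antiviral effect, with two stated hypotheses. MP0420 has 485 infused participants (Appendix G), and the comparisons are split further by nAb status. The primary, safety and ordinal analyses all use pharmacy, and the SAP gives no reason for leaving it out of section 12.

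**Working it through.** Sections 12.2-12.3 state no sample size, standard deviation, effect size or power, so there is no plan figure to reproduce.

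**Inputs from the documents:** N = 485 infused (Appendix G); 1:1 allocation (1.3); two-sided 5% tests and 95% intervals (section 3).

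**Assumptions:** r, the share of residual variance due to pharmacy after covariate adjustment; the number and sizes of pharmacies; blocks of 4.

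**1. ANCOVA, by formula.** Omitting pharmacy multiplies the model-based SE by f = 1/√(1−r). Actual type I error is 2[1−Φ(1.96f)]. For an effect that the pharmacy-adjusted model detects with 80% power, power becomes Φ(1.960 + 0.842 − 1.960f).

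Example at r = 0.10: f = 1/√0.90 = 1.054; power = Φ(2.802 − 2.066) = Φ(0.736) = 76.9%.

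| r | CI width | Type I error | Power |
|---|---|---|---|
| 0 | ×1.00 | 5.0% | 80.0% |
| 0.02 | ×1.01 | 4.8% | 79.4% |
| 0.05 | ×1.03 | 4.4% | 78.5% |
| 0.10 | ×1.05 | 3.9% | 76.9% |
| 0.20 | ×1.12 | 2.8% | 72.9% |

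**2. ANCOVA, by simulation.** With seven strata of assumed sizes 60/50/45/130/60/60/80 (total 485) and 4,000 runs, the mean SE was 0.0908 without strata and 0.0862 with strata at r = 0.10. The ratio is 0.0862/0.0908 = 0.949, equal to √0.90. With 30 unequal pharmacies and those under 20 participants pooled (1,000 runs), pooling recovered only part of the loss: power without and with pooled strata was 77.9% and 78.8% at r = 0.05, and 77.1% and 79.2% at r = 0.10.

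**3. Per-day logistic models, by simulation.** True conditional log OR 0.6, 30 pharmacies, 600 runs per setting, r on the latent logistic scale. Each cell shows pharmacy omitted, then pooled strata added.

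| r | Mean log OR | Median SE | Power | Rejection under the null |
|---|---|---|---|---|
| 0.05 | 0.58, 0.61 | 0.203, 0.207 | 82.7%, 83.3% | 5.3%, 6.5% |
| 0.10 | 0.56, 0.60 | 0.202, 0.209 | 79.2%, 81.2% | 4.7%, 4.7% |
| 0.20 | 0.51, 0.58 | 0.199, 0.212 | 75.3%, 78.0% | 4.3%, 5.2% |

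The Monte Carlo standard error of a 5% rejection rate is √(0.05×0.95/600) = 0.9 points, so the null column shows little. Adding strata makes the log-OR interval slightly wider. Power still rises, because the estimate is less attenuated.

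A separate indicator for every pharmacy overshoots: at r = 0 the mean log OR was 0.64 against a true 0.60, compared with 0.62 for pooled strata.

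**4. Slope comparisons (GEE in 12.2, mixed models in 12.3).** A slope over time is a within-participant contrast, and a pharmacy main effect should change it little. This is reasoned, not simulated. No figures were computed within nAb subgroups.

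**The case against.** The strongest reply is that this is an optional precision gain and not an error. That largely stands. The section 3 and 8.3 rules do not reach these outcomes, so nothing is contradicted. The general rule for subgroup analyses in 9.1 also stratifies by severity alone. Mean nAb and anti-N analyses are labelled exploratory (end of 12.3). Sparse strata are a genuine difficulty, since AZD7442 enrolled at 99 sites (E-5).

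The size is also uncertain. The documents give no between-pharmacy variance, the full-population antigen comparison already adjusts for nAb status, and assays were run centrally (Appendix F), which removes local-laboratory variation as a source.

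A reader might infer that every interval in 12.2-12.3 is too wide and every test runs below 5%. That holds only for the ANCOVA comparisons, which are secondary for antigen. The antigen hypotheses are addressed by logistic and GEE models, where omission gives a narrower log-OR interval or should matter little.

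A reader might also infer that the severity indicator itself costs precision, or that it is known to be constant for MP0420. A constant covariate simply drops out, and the documents establish constancy for AZD7442 only.

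What the reply does not remove is that a factor already collected and balanced by design goes unused, at some cost in power if sites differ.

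**Conclusion.** The point holds as a minor one. If pharmacy explains part of the residual variance, the ANCOVA comparisons are mildly conservative and lose about 1 to 3 power points at r of 2% to 10%. The per-day logistic comparisons pay through an odds ratio pulled toward 1 and a similar power loss at r of 5% to 20%. The slope contrasts are probably little affected.

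The omission causes neither confounding bias nor an excess of false positives, so no positive finding from these models would be undermined. All sizes rest on assumed values of r, pharmacy sizes and block size. If r is zero there is no loss.

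**What to change.** In 12.2 and 12.3, add site-pharmacy strata as a categorical covariate in the ANCOVA and per-day logistic models, overall and within antibody-status subgroups.

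- For AZD7442, use the seven strata of E-5, each built to hold at least 20 nAb-negative participants.
- For MP0420, Appendix G defines no strata. Form them under the section 3 pooling rule from blinded baseline data, before unblinding; section 1.1 already provides for SAP updates at that stage.
- Pool further where antigen-negative or antibody-positive counts are sparse, and do not use a separate indicator for every pharmacy.
- Keep the severity indicator only if both strata were enrolled, and say in Appendix G which case applies.

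The cost is SAP wording and one covariate, with no new data. The downsides are a few degrees of freedom and a slightly wider log-OR interval in the logistic models.
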